**Clinical Investigational Plan**

	paradigm according to group assignment	
--	--	--

**6.6 FOLLOW UP VISIT 3**

During the Third follow up visit, the investigator will collect the pain diary provided during the second follow up visit and record current stimulation parameters in the parameters form. The subject will evaluate the pain relief and their quality of life provided by the third stimulation paradigm using the VAS, EQ-5D questionnaires respectively. Subjects will also express preference between the three stimulation paradigms. The investigator will program the subject with the stimulation paradigm of choice and will return the patient programmer. The subject will then exit the study.

**6.7 UNSCHEDULED VISITS**

An Unscheduled Visit is defined as any visit where an active study subject returns to the participating study site for medical care outside of a specified study visit. Unscheduled visits may include subjects returning to the office for an adverse event.

The visit should be documented by completing the Unscheduled Visit Form and any other applicable forms (Adverse Event, Deviation, Death and/or Withdrawal Form).

**6.8 DESCRIPTION OF ACTIVITIES PERFORMED BY SPONSOR REPRESENTATIVES**

Trained sponsor personnel may perform certain activities to ensure compliance to the clinical investigational plan and may provide technical expertise.

Sponsor personnel may:

- Provide technical support to the Investigators during trial

Sponsor personnel will not:

- Perform the informed consent process
- Provide medical diagnosis or treatment to subjects
- Discuss a subject’s condition or treatment with a subject without the approval and presence of a health care practitioner
- Independently collect clinical investigational

**6.9 SUBJECT STUDY COMPLETION**

When the subject’s participation in the clinical study has been completed the subject will return to the medical care as per physician’s recommendation.

**6.10 ANY KNOWN OR FORSEEABLE FACTORS THAT MAY COMPROMISE THE OUTCOME OF THE CLINICAL STUDY OR THE INTERPRETATION OF THE RESULTS**

All foreseeable factors that may compromise the outcome have been taken into account by clinical study design and well-defined subject selection criteria.

## Clinical Investigational Plan

Patient recruitment and retention will be monitored throughout the study and include (but are not limited to) the following activities: evaluation of the site and investigators, training of site personnel, developing site support materials, providing patient visit calendars.

### 6.11 CRITERIA AND PROCEDURES FOR SUBJECT WITHDRAWAL OR DISCONTINUATION

Each subject should remain in the study until completion of the required follow up period; however, a subject's participation in the study may be discontinued at any time. Should this occur, the reason for discontinuation must be documented in the withdrawal form.

Subjects must be informed about their right to withdraw from the study at any time and for any reason without sanction, penalty or loss of benefits to which the subject is otherwise entitled and withdrawal from the study will not jeopardize their future medical care or relationship with the investigator. Subjects will be asked to specify the reason for the termination, but have the right not to answer.

The investigator may decide to withdraw a subject from the study at any time with reasonable rationale. The subject's future care will not be influenced by a decision, voluntary or otherwise, to withdraw from the study. All reasonable efforts should be made to retain the subject in the clinical study until completion of the study.

Reasons for subject's withdrawal include, but are not limited to:

- Subject refuses to continue participating in the study
- Subject does not meet the inclusion/exclusion criteria and does not require additional follow-up for safety reasons.
- Subject is deceased (cause must be documented)
- Subject's non-compliance
- Subject's participation is terminated by the PI or investigator, although the subject consented, since participation is no longer medically appropriate
- Subject is 'lost to follow up': Subject does not adhere to the scheduled follow up visits but has not explicitly requested to be withdrawn from the clinical study. (This does not apply to missed visits). Site personnel should at all times make all reasonable efforts to locate and communicate with the subject in order to achieve subject compliance to the scheduled follow up visits:
  1. A subject will be considered 'Lost to Follow Up' after a minimum of 2 phone calls of a physician or delegate at the investigational site to the subject or contact. These 2 phone calls need to be documented in the subject's hospital records.
  2. If these attempts are unsuccessful, a letter should be sent to the subject's last known address or general practitioner (GP) and a copy of this letter should be maintained in the subject's hospital records.

Note: If a subject misses one or more of the scheduled follow up visits (inclusive of the assigned visit windows), this will be considered as a missed visit. If subject misses a visit, the subject will be asked to fill the one week pain diary again and the latest pain diary will be used for analysis. The subject may therefore still return for subsequent visits and will not be excluded from the study.

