**Clinical Investigational Plan**

[figure not shown]
	
Exclusion Criteria
 
 
• Subject is currently participating in a clinical investigation study that includes an active treatment arm;
 
• Subject is currently receiving, applying or considering seeking workers compensation, or is involved in disability litigation;
 
• Subject has a non SJM neuromodulation device
 

Data Collection	
Subsequent to receiving the informed consent, subjects will be screened for inclusion/exclusion criteria. Eligible subjects will be randomized 1:1:1 to one of the treatment groups and be programmed accordingly. Subjects will be provided with a one-week diary to assess the pain relief provided by the first stimulation paradigm.
 
During the first follow up visit, the subjects will evaluate the pain level experienced during standard burst stimulation using the Visual Analog Scale (VAS), the European Quality of Life-5 Dimension (EQ-5D) questionnaire and the subject satisfaction questionnaire. Subjects will be programmed to the second stimulation paradigm and will be provided with a one-week pain diary.
 
During the second follow up visit, subjects will evaluate the efficacy of the second stimulation paradigm using the same assessments used in the first follow up visit. Subjects be programmed with the third stimulation paradigm and will be provided with a one-week pain diary.
 
During the third follow up visit, subjects will evaluate the efficacy of the last stimulation paradigm using the same assessments used in previous follow up visits. Additionally, subjects will be asked to express their preference between the three stimulation paradigms.
 
Occurrence of adverse events will be recorded through the study duration.

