## 4.4 ENDPOINTS

### 4.4.1 Primary Endpoint

Changes in Visual Analog Scale (VAS) scores between baseline and follow up visits

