## Clinical Investigational Plan

### 6.2 PROCEDURES

The clinical study will be conducted in accordance with the CIP. All parties participating in the conduct of the clinical study will be qualified by education, training, or experience to perform their tasks and this training will be documented appropriately.

The clinical study will not commence until St. Jude Medical receives written approval from the EC and relevant regulatory authorities and all required documents have been collected from the site(s).

Table 1: List of all study specific activities/procedures

Study Activity	Visit	Screening	Follow up visit 1	Follow up visit 2	Follow up visit 3
Informed Consent		X			
Inclusion/Exclusion Criteria Screening		X			
Randomization		X			
Sequester patient programmer		X			
Return patient programmer					X
Provide pain diary		X	X	X	
Collect pain diary			X	X	X
VAS assessment			X	X	X
EQ-5D questionnaire			X	X	X
Subject satisfaction questionnaire			X	X	X
Collect programming parameter printouts			X	X	X
Stimulation reprogramming		X	X	X	
Document patient preference					X
Program preferred stimulation paradigm					X

Table 2: Visits Timeline

Visit	Screening	Follow up visit 1	Follow up visit 2	Follow up visit 3
Timing	At enrollment	14±5 days after screening visit	14±5 days after follow up visit 1	14±5 days after follow up visit 2

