### Clinical Investigational Plan

Enrollment activities must be performed before any other study procedure/visit. Enrollment information (name of the study, date of consent) should be recorded in the clinic records, and the Enrollment form should be completed and submitted in a timely manner (recommended within 5 days). Notification of enrollment to the sponsor will take place only when the sponsor receives the Enrollment form.

In case the subject was consented, but does not meet inclusion/exclusion criteria, the following actions will be taken:

If additional study procedures have not occurred:

- Document enrollment information (name of the study, date of consent) and inclusion/exclusion information in the clinic and/or study records; complete the Enrollment Form and all forms for the Screening visit. The forms must be authorized / approved by the principal or delegated investigator.
- The EC should be notified appropriately about any deviations with regards to obtaining the informed consent.

If additional study procedures have occurred:

- Document enrollment information (name of the study, date of consent) and inclusion/exclusion information in the clinic and/or study records; complete the Enrollment Form, all forms for the Screening visit, and the Withdrawal Forms. The forms must be authorized / approved by the principal or delegated investigator.
- Complete study deviation for inclusion/exclusion not met.
- The EC should be notified appropriately about any deviations with regards to obtaining the informed consent.

If the subject meets the inclusion/exclusion criteria, the patient programmer will be sequestered and the subjects will be provided a one-week pain diary. Subjects will be randomized to one of the three treatment groups and their stimulator will be programmed with the first stimulation paradigm according to the group assignment. Stimulation intensity will gradually be increased until the subject perceives the stimulation to find the Threshold for Perception (TP), and then the intensity will subsequently be reduced to the sub-perception level providing optimal pain relief. Subjects will then receive a one-week pain diary to assess the pain levels during the first assigned stimulation paradigm. One week after this visit, the subject will be contacted to schedule the first follow up visit and instructed to start recording pain levels on the pain diary.

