## Clinical Investigational Plan

### 6.4 FOLLOW UP VISIT 1

During the baseline visit, the investigator will collect the pain diary provided at the screening visit and record the current stimulation parameters in the parameters form. The subject will rate the pain during the first stimulation paradigm using the VAS, the EQ-5D and the satisfaction questionnaires administered by a clinician blinded to the stimulation paradigm. Subject’s stimulators will be programmed with the second stimulation paradigm according to the group assignment. Stimulation intensity will gradually be increased until the subject perceives the stimulation to find the Threshold for Perception (TP), and then the intensity will subsequently be reduced to the sub-perception level providing optimal pain relief. Subjects will be provided with a new pain diary for the assessment of the new stimulation paradigm. One week after this visit, the subject will be contacted to schedule the second follow up visit and instructed to start recording pain levels on the pain diary

The following activities and assessments will be performed during the first follow up visit.

Timing of visit	Activities at visit	Case Report Form
Follow up 1	
 
Collect pain diary
 
Programming parameters printout
 
Subject fills out pain assessment and quality of life questionnaires
 
Provide pain diary
 
Program IPG with second stimulation paradigm according to group assignment
 
	
 
VAS Form
 
EQ-5D Form
 
User Satisfaction Form
 
Parameters Form
 

### 6.5 FOLLOW UP VISIT 2

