### 12.0 STATISTICAL CONSIDERATIONS

#### 12.1 STATISTICAL DESIGN, HYPOTHESES, METHOD AND ANALYTICAL PROCEDURES

During baseline visit subjects will be randomized 1:1:1 to one of the three treatment sequences. An envelope-based system will be used for identifying which group the subject has been assigned. St. Jude Medical will provide sealed envelopes containing the site number and subject ID/sequence number. Inside the envelope, the randomization assignment will be identified along with the site number and subject ID/sequence number.

During reprogramming the subjects will not be made aware of what paradigm is currently being programmed. Pain questionnaires (VAS, EQ-5D, satisfaction and stimulation preference) will be administered by a clinician blinded to the currently programmed stimulation paradigm.

Scores from the subject's questionnaires as well as subject satisfaction will be compared between follow up visits using a repeated measure ANOVA under the hypothesis of equivalence between standard and burst microdosing stimulation paradigms.

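### No VAS is scheduled for a subject who withdraws between visits, and the planned repeated-measures ANOVA in its classical form drops that subject, so withdrawal for poor relief would pull the estimate towards equivalence

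*Combined protocol and SAP*

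**What the plan says.** - **Endpoint.** Section 4.4.1 defines the primary endpoint as "Changes in Visual Analog Scale (VAS) scores between baseline and follow up visits".
- **Schedule.** In section 6.2, Table 1, the row "VAS assessment" is marked at follow-up visits 1, 2 and 3 only. There is no early-withdrawal column.
- **Order within a visit.** Section 6.4 has "The subject will rate the pain during the first stimulation paradigm using the VAS", followed by programming of the second paradigm. Section 6.5 follows the same order. Under section 6.3 "the patient programmer will be sequestered and the subjects will be provided a one-week pain diary", so subjects cannot change paradigm themselves between visits.
- **Missed visit.** Section 6.11 keeps the subject in the study and says "the subject will be asked to fill the one week pain diary again and the latest pain diary will be used for analysis". It does not mention the VAS.
- **Withdrawal.** Section 6.11 asks for the reason and, in the paragraph on adverse events, the subject's condition. The forms listed in section 6.7 for an unscheduled visit do not include the VAS form. Appendix H keeps all case report forms under separate cover.
- **Analysis.** Section 12.1 says that questionnaire scores and "subject satisfaction will be compared between follow up visits using a repeated measure ANOVA". The same sentence frames this comparison as one made "under the hypothesis of equivalence between standard and burst microdosing stimulation paradigms". It gives no analysis set and no rule for missing data.
- **Drop-out.** Section 12.2 expects none, plans for 30 completers, and states that the study is meant to yield estimates of the effect size.

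**The concern.** Section 3.0 names poorer relief as a possible result of the new settings, and subjects have no programmer with which to adjust therapy. Withdrawal is one way out of poor relief. A subject who takes it between visits leaves no scheduled VAS for the paradigm that prompted it, and a classical repeated-measures ANOVA also discards the VAS scores already given. The worst readings on the less effective paradigm are then the ones most likely to be missing.

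The output at stake is the effect estimate that section 12.2 says the study exists to provide. The distortion runs towards no difference, which is the hypothesis section 12.1 works under. An exit reading has to be planned in advance, because it cannot be recovered once the subject has left.

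**Working it through.** **What the plan gives.** It gives 30 completers, three sequences allocated 1:1:1, and no expected drop-out. It gives no SD, effect, equivalence margin or loss rate, so there is no figure of the plan's to reproduce. Everything below rests on assumptions.

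**Assumptions.** True losses against standard burst are 5 mm (5:5) and 10 mm (5:10). The SD of within-subject differences is 20 mm, so the per-period SD is σ = 20/√2 = 14.14 mm. The between-subject SD is 20 mm. A subject withdraws in the first period in which pain exceeds a threshold c, and that period's VAS is lost. Two triggers are compared: pain relative to the subject's own usual level, and absolute pain.

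**Standard error with 30 complete.** 20/√30 = 3.65 mm (2.74 at SD 15, 4.56 at SD 25).

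**Relative trigger, 7 of 30 lost, by hand.** Take c = 25.3 mm. For a paradigm with true mean μ, let a = (c − μ)/σ. The probability of leaving is 1 − Φ(a), and the mean among those retained is μ − σφ(a)/Φ(a).

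| Paradigm | μ | a | P(leave) | Downward shift (mm) |
|---|---|---|---|---|
| Standard | 0 | 1.79 | 0.037 | 1.18 |
| 5:5 | 5 | 1.44 | 0.076 | 2.18 |
| 5:10 | 10 | 1.08 | 0.140 | 3.65 |

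- Retained through all three periods: 0.963 × 0.924 × 0.860 = 0.766, so 23.4% are lost, about 7 of 30.
- 5:10 minus standard: 10 − 3.65 + 1.18 = 7.53 mm.
- 5:5 minus standard: 5 − 2.18 + 1.18 = 4.00 mm.
- Lost in period 1, with no scheduled VAS at all: (0.037 + 0.076 + 0.140)/3 = 0.084, or 2.5 of 30.

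**Complete-case estimate of the 10 mm difference over both triggers** (simulation error about 0.05 mm):

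| Lost of 30 | Relative trigger (mm) | Absolute trigger (mm) | Bias (mm) |
|---|---|---|---|
| 1 | 9.4 | 9.7 | 0.3 to 0.6 |
| 2 | 9.0 | 9.6 | 0.4 to 1.0 |
| 4 | 8.4 | 9.3 | 0.7 to 1.6 |
| 7 | 7.5 | 8.9 | 1.1 to 2.5 |

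At 7 lost the bias is 1.1/3.65 = 0.30 to 2.5/3.65 = 0.68 of a standard error. With no true difference the shifts are equal for all three paradigms and cancel.

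**What each remedy does at 7 of 30.**
- Mixed model on all available periods, no exit VAS: 7.5 mm (relative), unchanged from complete-case; 8.6 mm (absolute), slightly worse than the complete-case 8.9 mm.
- Mixed model plus an exit VAS from every leaver: 9.2 mm (relative), about 10.0 mm (absolute).
- Mixed model plus an exit VAS from half the leavers, relative trigger: 8.4 mm.
- For 5:5 under the relative trigger, full uptake moves 4.0 to 4.4 mm, recovering about 40% of the bias.
- If the exit reading correlates only 0.5 with the two-week reading (relative trigger), full uptake gives 10.3 mm, an overshoot of 0.3 mm. At correlation 0.8 it gives 9.7 mm.

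**The case against.** The case against is substantial.

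- **Size.** Every input is assumed. Section 12.2 expects no drop-out, and this is a feasibility study with no power claim. At 1 or 2 of 30 lost the bias is at most about 1 mm. This stands, and it limits how much weight the point can carry. It does not remove the point: random error shows in the confidence interval, whereas this bias does not, and it has a known direction.
- **Mechanism.** A reader might take 2.5 mm as the expected bias. It is the unfavourable end. It needs 7 of 30 lost and withdrawal driven by pain relative to the subject's own level. Under an absolute-pain trigger it is 1.1 mm.
- **Unseen forms.** A reader might infer that no pain score is recorded at withdrawal. The documents do not show that. The withdrawal form is under separate cover, nothing forbids a VAS, and a subject who leaves at a scheduled visit can still give one. What stands is that the plan neither schedules nor names one.
- **Missed visits.** A reader might infer that a missed visit loses the VAS for that paradigm. The plan largely answers this. The next paradigm is programmed at a visit, after the VAS, so a subject who misses a visit stays on the current paradigm and would naturally be rated at the next attendance. One clarifying sentence is enough.
- **Diary.** Nor is the diary without purpose. The synopsis says "Subjects will be provided with a one-week diary to assess the pain relief provided by the first stimulation paradigm", and section 6.11 says it will be analysed. What is missing is only a derived score and a place in sections 4.4 and 12.1.

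**Conclusion.** The point holds as a modest gap that should be closed. The plan schedules no VAS for a subject who withdraws between visits, and the classical form of its named analysis discards that subject. The result is bias towards equivalence if, and only if, a true difference exists and some withdrawals follow poor relief. Section 3.0 makes such loss plausible, not certain.

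Under the stated assumptions the bias on a 10 mm difference runs from 0.3 to 0.6 mm with one subject lost to 1.1 to 2.5 mm with seven, always below one standard error. Because the plan states no equivalence margin, this cannot be turned into a risk of a wrong conclusion.

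It is tempting to think that replacing the ANOVA by a mixed model would settle the matter. It would not. The lost readings depend on unobserved pain, so the model alone leaves the bias in place or makes it slightly worse. The exit reading does the work; the model lets that reading and the earlier periods be used. Confidence is medium, because the loss rate, SD and trigger are all unknown.

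**What to change.** 1. **Sections 6.7 and 6.11.** At withdrawal, where the subject agrees and without delaying care, complete the existing VAS and EQ-5D forms. They should be administered by the blinded clinician, as section 12.1 already requires, before any reprogramming or return of the programmer. Attribute them to the current paradigm, record the day within the period, and give a sensitivity analysis without them.
2. **Section 12.1.** Analyse the VAS by a mixed model with paradigm, period and sequence, using every available period from every randomised subject with at least one VAS.
3. **Minor clarifications.** State that after a missed visit the VAS is taken at the next attendance, before reprogramming. Name the per-paradigm diary mean as a supportive outcome, so that the diary rule in section 6.11 refers to a defined analysis.

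The cost is a few sentences, two existing forms completed once more per leaver, and entry of the diary data. Some exit readings will come before two weeks and may overshoot slightly. Some subjects will decline, so part of the bias can remain: under the relative trigger at 7 of 30, half uptake still leaves 10 − 8.4 = 1.6 mm.

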## Clinical Investigational Plan

If a subject withdraws from the clinical study, the site will record the subject's reasons for withdrawal, on a Withdrawal CRF.

When subject withdrawal from the clinical study is due to an adverse event the subject will be followed until resolution of that adverse event or determination that the subject's condition is stable. The status of the subject's condition should be documented at the time of withdrawal.

### 7.0 COMPLIANCE TO CIP

#### 7.1 STATEMENTS OF COMPLIANCE

The study will be performed in accordance with the most current versions of the World Medical Association (WMA) Declaration of Helsinki, ISO14155 and any regional and/or national regulations and will be compliant to this International Standard and any regional and national regulations, as appropriate.

The investigator will not start enrolling subjects or requesting informed consent from any subject prior to obtaining EC approval and Competent Authority approval, if applicable, and authorization from the sponsor in writing for the study.

In case additional requirements are imposed by the EC or Competent Authority, those requirements will be followed, if appropriate. If any action is taken by an EC, and regulatory requirements with respect to the study, that information will be forwarded to St. Jude Medical.

As sponsor, St. Jude Medical has taken up general liability insurance in accordance with the requirements of the applicable local laws. Appropriate country representative will be utilized to understand the requirements for the type of insurance that will be provided for subjects, such information will be incorporated into the informed consent, as applicable

If required, additional subject coverage or a study specific insurance will be provided by the Sponsor as well.

